### 7.4 Interim Analysis

No interim analyses of efficacy will be conducted.

An independent Data Monitoring Committee (DMC) will be constituted for this study to monitor important aspects of study conduct, including safety results on an ongoing basis. The DMC will receive masked data (treatment “A” vs. treatment “B”) at pre-specified time points for their review of safety data throughout the conduct of the trial. DMC meeting frequency and conduct will be outlined in a separate DMC Charter. An independent, unblinded statistician will provide the committee with masked data for review, but will not be a member of the committee. In addition, a clinical representative from the Sponsor will be available during an open session of each meeting to help answer questions or relay additional information to the DMC as needed, but this individual will not be a voting member of the committee. All members of the DMC will treat study data, reports, meeting discussions, and conclusions as confidential.

## 7.5 Comments on the Statistical Analyses

- All clinical data will be provided in by-subject listings.
- Continuous variables will be summarized using number (N), mean, standard deviation (SD), median, minimum, and maximum.
- Frequency counts and percentages will be reported for all categorical data.
- If a laboratory result (other than an MIC value) is reported relative to a lower/upper range of detection for an assay, for example, “<10”, the numeric portion of the result (10) will be used for statistical analyses and the full result, including any symbols, will be provided in the subject listings.
- For AEs with onset on or after the first dose of study drug, onset day will be calculated as the date of onset of the AE minus the date of the first dose of study drug, plus 1. For AEs with onset prior to the first dose of study drug, onset day will be calculated as the date of onset of the AE minus the date of the first dose of study drug.
- For prior medications, start day will be calculated as the start date of the medication minus the date of the first dose of study drug (or date of randomization if no study drug was received). For concomitant medications and prior medications taken on the same day as the first dose of study drug (or date of randomization if no study drug was received), start day will be calculated as the start date of the medication minus the date of the first dose of study drug (or date of randomization if no study drug was received), plus 1.
- Version 9.2 (or higher) of SAS statistical software package will be used to provide all summaries, listings, figures and statistical analyses.

## 7.6 Handling of Missing Data

For ECR, missing data will be handled as follows:

- If any component of ECR is missing in the time frame detailed in Section 6.1 (unless the subject dies or is deemed a failure prior to this time point), or if the subject does not have at least 2 symptoms of CABP at baseline, ECR will be defined as an indeterminate.
- If the time of a post-baseline assessment of CABP symptoms obtained in the window for determination of ECR is missing but the date of the ECR assessment is known, the time will be imputed to noon on the date of the CABP symptom assessment. If the time of assessment of CABP symptoms obtained on or prior to the date of the first dose of study drug is missing, the time will be imputed to 00:00.
- Missing start and stop times of antibiotics will be set to 00:00 on the start and stop date of the antibiotic.
- For the analysis of ECR in the ITT Analysis Set, where ECR may be missing (indeterminate), all subjects in the ITT Analysis Set will be included in the denominator. Thus, subjects with an indeterminate response are essentially considered as a failure.

For IACR, missing data will be handled as follows:

- A missing IACR at the EOT Visit will be considered indeterminate at the EOT Visit.
- A missing IACR at the TOC Visit will be considered indeterminate unless the IACR at the EOT Visit is failure. An IACR of failure at the EOT Visit will be carried forward to the TOC Visit.
- A missing IACR at the LFU Visit will be considered indeterminate unless the IACR at the TOC Visit is failure. An IACR of failure at the TOC Visit will be carried forward to the LFU Visit.
- For the analysis of IACR at the EOT, TOC and LFU Visits in the mITT, microITT, microITT-2 and emicroITT Analysis Sets, where Clinical Response may be missing (indeterminate), all subjects who meet the analysis set criteria will be included in the denominator.
- For the analysis of IACR at the EOT, TOC and LFU Visits in the CE and ME Analysis Sets, subjects with a missing (indeterminate) IACR will not be included in the analyses, since by definition, subjects in the CE or ME Analysis Sets cannot have a missing IACR.

For microbiological response, missing data will be handled as follows:

- If a followup specimen for culture was not obtained, microbiological response at the EOT Visit will be determined based on the IACR at the EOT Visit.
- A by-pathogen microbiological response of persistence and a by-subject microbiological response of failure at the EOT Visit will be carried forward to the TOC Visit. If a followup specimen for culture was not obtained and the pathogen/subject was not a microbiologic persistence/failure at EOT, microbiological response at the TOC Visit will be determined based on IACR at the TOC Visit. If the IACR at the TOC Visit is indeterminate, the microbiological response at the TOC Visit will be indeterminate, unless a followup specimen for culture was obtained.
- A by-pathogen microbiological response of persistence and a by-subject microbiological response of failure at the TOC Visit will be carried forward to the LFU Visit. If a followup specimen for culture was not obtained and the pathogen/subject was not a microbiologic persistence/failure at TOC, microbiological response at the LFU Visit will be determined based on IACR at the LFU Visit. If the IACR at the LFU Visit is indeterminate, the microbiological response at the LFU Visit will be indeterminate, unless a followup specimen for culture was obtained.
- For the analysis of microbiological response at the EOT, TOC and LFU Visits in the microITT and microITT-2 Analysis Sets, where microbiological response may be missing (indeterminate), all subjects who meet the analysis set criteria will be included in the denominator.
- For the analysis of microbiological response at the EOT, TOC and LFU Visits in the ME Analysis Sets, subjects with a missing (indeterminate) microbiological response will not be included in the analysis, since by definition, subjects in the ME Analysis Sets cannot have a missing microbiological response.

For all other outcome measures, missing data are handled as follows:

- Missing values for individual data points will remain as missing. Missing values will not be imputed and only observed values will be used in data analyses and presentations.
- When individual data points are missing, categorical data will be summarized based on reduced denominators (ie, only subjects with available data will be included in the denominators).

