### 8.4.2 Prior and Concomitant Medications

The World Health Organization (WHO) drug dictionary will be used to classify prior and concomitant medications, including antibacterial medications, by therapeutic class. A prior medication is defined as any medication taken prior to the date and time of the first dose of study drug (or date of randomization if no study drug was received). For non-antibacterials (for which only start and stop dates [not times] are collected), any medication taken on or after the date of first dose of study drug (or date of randomization if no study drug was received) will be considered concomitant; medications stop dates occurring prior to the date of first dose of study drug (or date of randomization if no study drug was received) will be considered prior medications. A concomitant medication is defined as any medication taken on or after the date and time of the first dose of study drug (or date of randomization if no study drug was received).

If the start date of a medication is missing, the medication will be assumed to be both prior and concomitant, unless the end date of the medication clearly indicates the medication was stopped prior to the first dose of study drug (or date of randomization if no study drug was received). If the start date is a partial date such that it cannot be determined if the medication is prior or concomitant, the medication will be assumed to be both prior and concomitant, unless the end date of the medication clearly indicates the medication stopped prior to the first dose of study drug (or date of randomization if no study drug was received).

For antibacterials, missing start and stop times will be set to 00:00 on the start and stop date of the antibiotic.

Prior systemic antibacterial medications and concomitant systemic antibacterial medications will be summarized by Anatomical Therapeutic Chemical (ATC) level 4 (or the next available level if level 4 is not available) and preferred term separately by treatment group for the ITT, mITT and CE-TOC Analysis Sets. Subjects receiving the same medication more than once will be counted only once for a particular ATC level and preferred term. Prior systemic antibacterial medications will be summarized based on receipt within 72 hours prior to randomization and receipt more than 72 hours prior to randomization.

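### An untimed antibacterial dated only on the day of first dose is always classed as prior, so one given after study drug cannot count against Early Clinical Response

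*SAP*

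**What the plan says.** SAP 7.6, under missing data for ECR: "Missing start and stop times of antibiotics will be set to 00:00 on the start and stop date of the antibiotic". SAP 8.4.2 repeats it: "For antibacterials, missing start and stop times will be set to 00:00 on the start and stop date of the antibiotic".

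The classification in 8.4.2 works to the minute. "A prior medication is defined as any medication taken prior to the date and time of the first dose of study drug", and "A concomitant medication is defined as any medication taken on or after the date and time of the first dose of study drug". Neither section makes an exception for an untimed antibacterial on the date of first dose.

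Other gaps in 8.4.2 are handled differently. For non-antibacterials, which carry dates only, the concomitant class covers "any medication taken on or after the date of first dose of study drug". Where a start date is missing, or too incomplete to place, "the medication will be assumed to be both prior and concomitant", unless the end date shows that the drug stopped before study drug began.

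The class is used in two places that matter. SAP 6.1 makes a subject an ECR non-responder after a concomitant antibiotic for CABP. SAP 5.6 criterion 5 removes subjects from the CE sets for another active systemic antibacterial after first dose, unless it was given for clinical failure. SAP 8.4.2 also tabulates the recorded reason for each concomitant antibacterial. Two of the reasons refer to a condition present before randomization. The rest include insufficient effect of study drug, a treatment-limiting adverse event, a concomitant infection and other.

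Prior systemic antibacterials are "summarized based on receipt within 72 hours prior to randomization and receipt more than 72 hours prior to randomization".

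**The concern.** A missing time on the day of first dose leaves the order of the two drugs unknown. The rule settles that order as antibacterial first, without looking at any other evidence. A reason such as insufficient effect of study drug can only arise after study drug, yet a Day 1-only record carrying it would still be prior.

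At stake is a component of the primary endpoint. ECR is derived by program, so nothing later in the derivation would restore the antibiotic. The subject would be judged on symptoms alone and could be a responder while treated with a non-study drug. The handling is also uneven within 8.4.2. A missing start date is treated cautiously, and a non-antibacterial on the same date counts as concomitant. An antibacterial with a known date and no time does not, although antibacterials are the class that decides ECR.

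**Working it through.** **Inputs.** The 00:00 rule (SAP 7.6, 8.4.2); the definitions of prior and concomitant (8.4.2); 369 subjects per arm (SAP 7.1). The clock times below are assumed for illustration. The plan gives no figure of its own to reproduce here.

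**Step 1: the day of first dose.** Take the first study dose at 10:00 and an antibacterial actually given at 15:00.

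| Record | Imputed interval | Class under the rule | True class |
|---|---|---|---|
| Day 1 only, both times missing | 00:00 to 00:00, Day 1 | prior only | concomitant |
| Day 1 to Day 5, both times missing | 00:00 Day 1 to 00:00 Day 5 | prior and concomitant | concomitant |
| Day 1 only, start 15:00 known, stop missing | 15:00 to 00:00, stop before start | concomitant, by the known start | concomitant |

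The first row holds for any first dose later than 00:00. The second still counts for ECR and for CE criterion 5. The third is classed correctly if the program uses the start. A program that tests the imputed stop would place it in neither class, because 15:00 is not before 10:00 and 00:00 is not at or after 10:00.

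**Step 2: later days.** An untimed CABP antibiotic dated on the day of the symptom assessment is placed at 00:00, before the assessment, so the subject is a non-responder. Here the rule counts against response.

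**Step 3: when a Day 1 error changes a result.**
- ECR changes only if the symptom data otherwise meet the responder criteria. If no usable assessment exists, the subject is indeterminate, which the primary analysis already counts as non-response.
- For CE criterion 5, antibacterials given for clinical failure are not grounds for exclusion. A subject who stopped study drug on Day 1 already fails the 48-hour minimum in criterion 4, apart from deaths before 48 hours. What remains is mainly a one-day antibacterial for another infection or other reason while study drug continued.

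**Step 4: size.** One subject = 1/369 = 0.00271, or 0.27 percentage points of an arm's ECR rate.

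**Step 5: the 72-hour window.** Let randomization be at hour r and the dose at hour t, three calendar days earlier. The true gap is 72 + r − t hours, inside the window when t ≥ r. With t set to 0 the gap is 72 + r, which runs from 72.0 to 95.98 h. It exceeds 72 h for 1,439 of the 1,440 possible minutes of randomization; the exception is exactly 00:00. If true dose times were uniform over the day (an assumption), the share truly inside would be (24 − r)/24:

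- r = 08:00: 16/24 = 67%
- r = 12:00: 12/24 = 50%
- r = 18:00: 6/24 = 25%

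All of these would be shown as more than 72 hours. This applies to doses dated only on that day. An untimed course ending two calendar days before randomization has an imputed stop 48 to under 72 h before it, and stays inside.

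**The case against.** The strongest reply is that the rule usually gives the right answer. Protocol 5.3 allows up to 25% of subjects a single short-acting dose before randomization, about 184 of 738 (0.25 × 738 = 184.5). An untimed one-date record on Day 1 is most plausibly such a dose, and 00:00 classes it correctly. Protocol 6.8.2 ends study drug and assigns an IACR of failure when more antibiotic is needed for CABP, so replacement therapy confined to Day 1 would be unusual. Protocol 6.8 has start and stop times recorded for systemic antibacterials, and Protocol 15.5 has missing data queried. SAP 5.6 allows blinded manual review of CE membership. All of this stands and limits the number affected. It does not rescue the record whose stated reason contradicts the imputed order, and the manual review concerns CE membership, not the programmed ECR.

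A reader might infer that the rule always favours response. It does not: Step 2 shows the opposite on the assessment day. A reader might also infer that every untimed Day 1 antibiotic is lost. Only records that start and stop that day are.

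A further tempting reading is that the 72-hour error reaches the main results. The documents do not show this. CE exclusion criterion 1 comes from the Inclusion/Exclusion eCRF (SAP 5.6), the stratum results use the IRT, and the prior-antibiotic subgroup is per the eCRF (SAP 8.5.2). Nothing says that the sensitivity analysis on the correct stratum is derived from imputed times.

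Finally, the obvious remedy, a 23:59 stop for every missing stop time, would do harm. Take a permitted dose with a known start at 08:00, no stop time, and study drug at 14:00. The present rule makes it prior. A 23:59 stop would make it concomitant and could produce a false ECR non-response.

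**Conclusion.** The point holds in a narrow form. As written, the rule gives a wrong class to an untimed antibacterial dated only on the day of first dose when the drug was in fact given after study drug. Such a drug is lost to the ECR non-responder criterion and may be missed for CE criterion 5. The conclusion rests on the wording of SAP 7.6 and 8.4.2 applied literally, and on no exception being made in an Evaluability Review Plan that is not among these documents.

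The size is 0.27 percentage points of one arm's ECR rate per subject changed, against a 10-point margin. The number of such records is not given and should be small. The effect on the treatment difference depends on the arm in which they fall, so no direction of bias in the comparison is established. The 72-hour matter is minor and confined to the descriptive prior-antibiotic tables.

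**What to change.** In SAP 7.6 and 8.4.2:

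1. Keep 00:00 as the general rule. Do not introduce a blanket 23:59 stop.
2. For an antibacterial dated on the day of first dose, where a missing start or stop time leaves its order relative to that dose unknown, classify by the recorded reason. Either of the two reasons that refer to a condition before randomization (the current CABP, or an unrelated infection) makes it prior. Any other reason makes it both prior and concomitant.
3. Never impute a stop time earlier than a known start time.
4. In the 72-hour tables, show an untimed dose dated three calendar days before randomization as window undetermined, not as more than 72 hours.

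The second rule protects the permitted pre-study dose and uses reasons that 8.4.2 already tabulates. The cost is a few sentences in the SAP and a few lines of programming, with no new data. It should be settled before database lock and unblinding, since a later change would be post hoc.

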## **8.0 STATISTICAL ANALYSES**

### **8.1 Subject Disposition and Protocol Deviations**

The number of subjects randomized by region, country and center will be presented by treatment group in the ITT Analysis Set. The number of subjects included in each of the study analysis sets (ITT, mITT, Safety, emicroITT, microITT, microITT-2, CE-EOT, CE-TOC, CE-LFU, ME-EOT, ME-TOC and ME-LFU) will be summarized overall and by geographic region, for each treatment group and across treatment groups. Regions are defined as follows: North America (United States), Latin America (Argentina, Brazil, Chile, Mexico, Peru), Eastern Europe (Bulgaria, Georgia, Latvia, Russia, Serbia, Ukraine), Western Europe (Hungary, Poland, Spain) and Rest of World (Philippines, South Korea, Taiwan, South Africa). The reasons for exclusion from the mITT, Safety, emicroITT, microITT, microITT-2, CE and ME Analysis Sets will be tabulated. A by-subject listing will be provided that will include the reason(s) for exclusion from each of the study analysis sets.

A listing will provide the date of informed consent for all randomized subjects, whether or not the subject met all inclusion/exclusion criteria and if not, which criteria were not met. The number of subjects completing the study (ie, completing the LFU Visit), completing the EOT assessment, completing the TOC assessment, prematurely withdrawing from the study, completing study drug, prematurely discontinuing study drug, and the reasons for premature withdrawal and premature discontinuation will be summarized by treatment group and overall for all subjects in the ITT Analysis Set. The percentages of subjects discontinued from study drug and prematurely withdrawn from the study will be compared between treatment groups using Fisher's exact test. A listing of study completion/premature withdrawal and study drug completion/premature discontinuation for all subjects will be provided and will display subject ID, treatment, the primary reason for premature withdrawal or discontinuation, date and study day of last study visit, and vital status at Day 28.

The number and percentage of subjects in the ITT Analysis Set with at least 1 significant protocol deviation will be summarized by treatment group and overall. A significant protocol deviation is one that has the potential to affect efficacy assessments, placement into analysis populations, the safety or ability to monitor the safety of a subject, or the scientific value of the trial. The number and percentage of subjects with at least 1 significant deviation that excludes a subject from the CE Analysis Sets and the number and percentage of subjects with at least 1 other significant deviation will also be summarized by treatment group and overall, and by deviation subtype.

A by-subject listing of all significant protocol deviations will also be provided.

## 8.2 Demographics and Baseline Characteristics

Descriptive statistics for continuous variables (age, height, weight, and body mass index), and frequency counts and percentages for categorical variables (age group, race, ethnicity, gender and renal status [severe impairment [ $<30$  mL/min], moderate impairment [ $30$ - $<60$  mL/min], mild impairment [ $60$ - $<90$  mL/min] and normal function [ $\geq 90$  mL/min]) will be summarized by treatment group and overall for the ITT, mITT and CE-TOC Analysis Sets. Body mass index will be calculated by dividing weight (kg) by height ( $m^2$ ). Creatinine clearance based on the central lab determination will be used. In those cases where creatinine clearance is not available from the central lab, it will be calculated using the local lab serum creatinine based on the Cockcroft-Gault equation:

$$\frac{(140 - \text{age}[\text{yrs}]) * \text{weight}[\text{kg}] * (Z)}{\text{Cr}[\text{mg/dL}] * 72} \quad \begin{array}{l} Z = 1.0, \text{ if Male} \\ Z = 0.85, \text{ if Female} \end{array}$$

A table will provide the frequency counts and percentages by treatment group and overall for PORT Risk Class (both as per IRT [II, III/IV] as well as calculated from components reported in the eCRF [II, III/IV]), subjects meeting minor and modified American Thoracic Society (ATS) severity criteria, subjects meeting the Systemic Inflammatory Response Syndrome (SIRS), CURB-65 category and subjects with bacteremia for the ITT, mITT and CE-TOC Analysis Sets. PORT score and CURB-65 Score will also be summarized as a continuous variable. CURB-65 is derived from the eCRF data and ranges from 0-5 where 1 point is given for each of the following at baseline:

- Confusion (defined as altered mental status as recorded on the PORT Risk Assessment eCRF)
- blood urea nitrogen (BUN)  $>19$  mg/dL ( $>6.8$  mmol/L)
- respiratory rate  $\geq 30$  breaths/min,
- systolic blood pressure  $<90$  mmHg or diastolic blood pressure  $\leq 60$  mmHg
- age  $\geq 65$  years.

ATS severity and SIRS criteria are derived from the eCRF data and baseline PMNs reported in the central safety laboratory data. The minor ATS severity criteria is defined as presence of  $\geq 3$  of the following 9 criteria at baseline:

- respiratory rate  $\geq 30$  breaths/min
- $O_2$  saturation  $<90\%$  or  $PaO_2 <60$  mmHg
- BUN  $\geq 20$  mg/dL
- WBC  $<4000$  cells/ $mm^3$
- confusion
- multilobar infiltrates (defined as infiltrates present in any two locations, except lingula and left upper lobe is not multilobar. Lingula and other location is multilobar)
- platelets  $<100,000$  cells/ $mm^3$
- temperature  $<36^\circ C$
- systolic blood pressure  $<90$  mmHg.

Modified ATS severity criteria is defined as presence of  $\geq 3$  of the following 6 criteria at baseline:

- respiratory rate  $\geq 30$  breaths/min
- $\text{SpO}_2/\text{FiO}_2 < 274$  where  $\text{SpO}_2/\text{FiO}_2 = 64 + 0.84 (\text{PaO}_2/\text{FiO}_2)$
- $\text{BUN} \geq 20$  mg/dL
- Confusion
- Age  $\geq 65$  years
- multilobar infiltrates.

SIRS criteria is defined as  $\geq 2$  of the following 4 symptoms at baseline:

- temperature  $< 36^\circ\text{C}$  or  $> 38^\circ\text{C}$
- heart rate  $> 90$  beats/min
- respiratory rate  $> 20$  breaths/min
- $\text{WBC} < 4000$  cells/ $\text{mm}^3$ , or  $\text{WBC} > 12,000$  cells/ $\text{mm}^3$ , or immature PMNs  $> 10\%$ .

Baseline assessments of clinical signs and symptoms of CABP, including fever (defined as body temperature  $> 38.0^\circ\text{C}$  ( $100.4^\circ\text{F}$ ) oral, tympanic  $> 38.5^\circ\text{C}$  ( $101.3^\circ\text{F}$ ), rectal/core  $> 39.0^\circ\text{C}$  ( $102.2^\circ\text{F}$ ), or axillary  $> 37.5^\circ\text{C}$  ( $99.5^\circ\text{F}$ )), hypothermia (defined as body temperature  $< 35.0^\circ\text{C}$  ( $95.0^\circ\text{F}$ ) oral, tympanic  $< 35.5^\circ\text{C}$  ( $95.9^\circ\text{F}$ ), or rectal/core  $< 36.0^\circ\text{C}$  ( $96.8^\circ\text{F}$ )), hypotension (systolic blood pressure  $< 90$  mmHg), tachycardia (heart rate  $> 100$  beats/min), tachypnea (respiratory rate  $> 20$  breaths/min), dyspnea, cough, production of purulent sputum and chest pain will be summarized by treatment group and overall for the ITT, mITT and CE-TOC Analysis Sets.

Medical history (including diseases/conditions and surgical procedures) will be summarized by treatment group and overall for subjects in the ITT Analysis Set. For the summary of medical history, subjects with more than 1 abnormality within the same preferred term will be counted only once for that preferred term. Subjects are counted only once in a system organ class.

CABP risk factors, including tobacco history (current and previous use of cigarettes, cigars, chewing tobacco and other), history of pneumococcal vaccination, evidence of influenza during the current illness and history of influenza vaccination, will be summarized by treatment group and overall for subjects in the ITT, mITT and CE-TOC Analysis Sets.

Readings of baseline chest radiographs by the radiologist, including the type of assessment (chest X-ray or CT scan), radiographic evidence of CABP (ie, a pulmonary infiltrate or diffuse opacity), presence of pleural effusion, whether the pleural effusion is unilateral or bilateral, presence of pulmonary infiltrate, whether the pulmonary infiltrate was uni- or multi-lobar, the location of the pulmonary infiltrate(s), presence of diffuse opacities and the location of the diffuse opacities will be summarized by treatment group and overall for all subjects in the ITT, mITT and CE-TOC Analysis Sets.

Descriptive statistics of baseline procalcitonin and number and percentage of subjects in the categories  $< 0.1$  mcg/L,  $0.1$  mcg/L to  $0.25$  mcg/L and  $> 0.25$  mcg/L will be presented by treatment group and overall for the ITT, mITT and CE-TOC Analysis Sets.

